# 5.2.4 Genetic Counseling

If the research findings are verified in the CLIA certified lab, the subject will be referred to a genetic healthcare provider within the NIH for the disclosure of the results. These activities will be funded by the Center for Cancer Research.


Please e-mail **Blood Processing Core (BPC)** ([name]) at [contact] at least 24 hours before transporting samples (the Friday before is preferred).

For sample pickup, page [name]. Samples are to be delivered to the [name] Lab (4B11).

For immediate help, call [contact] (main blood processing core number) or, if no answer, [contact] (main clinical pharmacology lab number).

For questions regarding sample processing, contact BPC by e-mail at [contact].

- All samples sent to the Blood Processing Core (BPC) will be barcoded, with data entered
  and stored in the Labmatrix utilized by the BPC. This is a secure program, with access to
  Labmatrix limited to defined BPC personnel, who are issued individual user accounts.
  Installation of Labmatrix is limited to computers specified by [name]. These computers
  all have a password restricted login screen.
- Labmatrix creates a unique barcode ID for every sample and sample box, which cannot be traced back to patients without Labmatrix access. The data recorded for each sample includes the patient ID, name, trial name/protocol number, time drawn, cycle time point, dose, material type, as well as box and freezer location. Patient demographics associated with the clinical center patient number are provided in the system. For each sample, there are notes associated with the processing method (delay in sample processing, storage conditions on the ward, etc.).
- Barcoded samples are stored in barcoded boxes in a locked freezer at either -20 or -80°C according to stability requirements. These freezers are located onsite in the BPC and offsite at NCI Frederick Central Repository Services in Frederick, MD. Visitors to the laboratory are required to be accompanied by laboratory staff at all times.
- Access to stored clinical samples is restricted. Samples will be stored until requested by a researcher named on the protocol. All requests are monitored and tracked in Labmatrix.

Version Date: 01/01/2024

All researchers are required to sign a form stating that the samples are only to be used for research purposes associated with this trial (as per the IRB approved protocol) and that any unused samples must be returned to the BPC. It is the responsibility of the NCI Principal Investigator to ensure that the samples requested are being used in a manner consistent with IRB approval.

- Following completion of this study, samples will remain in storage as detailed above. Access to these samples will only be granted following IRB approval of an additional protocol, granting the rights to use the material.
- If, at any time, a patient withdraws from the study and does not wish for their existing samples to be utilized, the individual must provide a written request. Following receipt of this request, the samples will be destroyed (or returned to the patient, if so requested). The PI will record any loss or unanticipated destruction of samples as a deviation. Reporting will be per the requirements of section 7.2.
- Sample barcodes are linked to patient demographics and limited clinical information. This information will only be provided to investigators listed on this protocol, via registered use of Labmatrix. It is critical that the sample remains linked to patient information such as race, age, dates of diagnosis and death, and histological information about the tumor, in order to correlate genotype with these variables.
- 5.3.3 Samples processing in the Department of Laboratory Medicine and NCI Laboratory of Pathology.
  - Biopsy, bone marrow or peripheral blood samples will be obtained from the Hematopathology Section of the NCI Laboratory of Pathology (LP) or the Hematology Section (HS) of the DLM, CC.
  - Samples are coded by the LP HS, DLM HS or [name] Lab. Tissue sections, or peripheral blood samples will be obtained and stored in the [name] lab or LP Proteomics Core lab without any personal identifiers and will be labeled with the anonymous LP HS or DLM HS sample accession ID number.
  - The relationship between the accession ID number and the patient clinical information will be stored in a secure database that is maintained and regularly backed up by Drs. [name], [name], or [name].
  - The [name] laboratory or LP Proteomics Core Lab will prepare tissue lysates, RNA and DNA from each sample. Samples, lysates and derived biologic molecules will be stored in Eppendorf tubes marked with the sample accession ID number in locked -80° C freezers in the [name] laboratory or LP Proteomics Core Lab.

## 5.3.4 Protocol Completion & Sample Destruction

Any specimens that are remaining at the completion of the protocol will be stored in the conditions described above.

The principal investigator will record the following:

- Destroyed samples which become unsalvageable because of environmental factors (ex. a broken freezer or lack of dry ice in a shipping container) or if a patient withdraws consent.
- Samples lost in transit between facilities or misplaced by a researcher.

Version Date: 01/01/2024

• All other problems associated with samples.

## 6 DATA COLLECTION AND EVALUATION

#### 6.1 DATA COLLECTION

The PI will be responsible for overseeing entry of data into a 21 CFR Part 11-compliant data capture system provided by the NCI CCR and ensuring data accuracy, consistency and timeliness. The principal investigator, associate investigators/research nurses and/or a contracted data manager will assist with the data management efforts. Primary and final analyzed data will have identifiers so that research data can be attributed to an individual human subject participant.

All adverse events (AEs), including clinically significant abnormal findings on laboratory evaluations, regardless of severity, will be followed until return to baseline or stabilization of the event.

Document AEs from the first study intervention from Study Day 1 through 30 days after the last dose of study drug. Beyond 30 days after the last intervention, only adverse events which are serious and related to the study intervention need to be recorded.

An abnormal laboratory value will be recorded in the database as an AE only if the laboratory abnormality is characterized by any of the following:

- Results in discontinuation from the study
- Is associated with clinical signs or symptoms
- Requires treatment or any other therapeutic intervention
- Is associated with death or another serious adverse event, including hospitalization.
- Is judged by the Investigator to be of significant clinical impact
- If any abnormal laboratory result is considered clinically significant, the investigator will provide details about the action taken with respect to the test drug and about the patient's outcome.

**End of study procedures:** Data will be stored according to HHS, FDA regulations and NIH Intramural Records Retention Schedule as applicable.

**Loss or destruction of data:** Should we become aware that a major breach in our plan to protect subject confidentiality and trial data has occurred, this will be reported expeditiously per requirements in section 7.2.1.

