# 1.1.2 Secondary Objectives

- To determine biochemical and symptomatic progression free survival (PFS)
- To determine duration of response (DOR)
- To determine duration of minimal residual disease (MRD) negative complete response (CR), and to estimate the rate of durable MRD(-) CRs (greater than one year)
- To evaluate toxicity of combination therapy (carfilzomib, lenalidomide, and dexamethasone)
- To evaluate biological activity of carfilzomib and correlate to clinical outcomes (gene expression profiling on pre- and post-carfilzomib exposure bone marrow samples) NOTE: This endpoint no longer applies as of Amendment H (version date 06/12/2017).
- To determine overall survival (OS)
- To compare the MRD (-) CR rates between patients enrolled from 2012-2014 vs. enrolled in 2017 and later years

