3.3.1 Dose Reductions: Induction Phase

	Lanalidamida	Carfilzamih	Dexamethasone	
	Lenalidomide	Carfilzomib	Cycles 1-4	Cycles 5-8
Baseline dose	25 mg daily on Days 1-21 of 28 day cycle	$36 \text{ mg/m}^2$	20 mg	10 mg
One level dose reduction	20 mg daily on Days 1-21 of 28 day cycle	27 mg/m 	10 mg	4 mg
Two level dose reduction	15 mg daily on Days 1-21 of 28 day cycle	20 mg/m 	4 mg	0 mg
Three level dose reduction	10 mg daily on Days 1-21 of 28 day cycle		0 mg	
Four level dose reduction	5 mg daily on Days 1-21 of 28 day cycle			

- 3.3.1.1 Lenalidomide and Carfilzomib dosages are not modified in concert; i.e., lenalidomide and carfilzomib dosage reductions are implemented separately. If more than 2 dose reductions are required with Carfilzomib, study treatment will be discontinued and the patient will go off therapy.
- 3.3.1.2 If there is no resolution of toxicity after 2 weeks of withholding treatment or up to 3 weeks for infection related treatment, the subject will go off therapy
- 3.3.2 Hematologic Toxicity: Induction Phase
- 3.3.2.1 Due to the nature of the disease originating in the bone marrow, events occurring within the first two cycles of treatment and deemed to be due to disease burden will be exempt from dose reductions at the discretion of the investigator.
- 3.3.2.2 On day 1 of each new cycle (or day 1 of every third cycle during extension phase), patients must meet the following criteria or dose modify based on dose reductions in table 3.3.1:
  - ANC  $> 1.0 \times 10^9 / L$
  - Platelet count  $\geq$  75 x 10^9/L during cycles 1-8; Platelet count  $\geq$ 50 x 10^9/L during cycles 9 and beyond

If these conditions are not met on Day 1 of a new cycle, a new cycle of treatment will not be initiated until the toxicity has resolved. If there is no resolution after 2 weeks of withholding treatment or up to 3 weeks for infection related treatment, the subject will go off therapy.

*Version Date:* 01/01/2024

If the investigator chooses to dose reduce according to table 3.3.1, the investigator will determine which drug will be modified based on side effect profile and clinical judgment.

3.3.2.3 If a patient develops thrombocytopenia or neutropenia during the cycle, then the following actions would take place (see Thrombocytopenia/Neutropenia table below).

Thrombocytopenia	Lenalidomide	Carfilzomib

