If Posterior Reversible Encephalopathy Syndrome (PRES) is suspected	If PRES is suspected, hold carfilzomib. Consider evaluation with neuroradiological imaging, specifically MRI, for onset of visual or neurological symptoms suggestive of PRES. If PRES is confirmed, permanently discontinue carfilzomib. If the diagnosis of PRES is excluded, carfilzomib administration may resume at same dose, if clinically appropriate.

Version Date: 01/01/2024

Carfilzomib Toxicities	Dosing Modifications
If thrombotic microangiopathy (TTP/HUS) is suspected	Hold carfilzomib and manage per standard of care including plasma exchange as clinically appropriate. If TMA is confirmed and related to carfilzomib, permanently discontinue carfilzomib. If the diagnosis is excluded, carfilzomib can be restarted at the previous dose. If the condition recurs, permanently discontinue carfilzomib.
Hepatic Impairment:	
Mild to moderate liver dysfunction: defined as 2 consecutive values, at least 28 days apart, of: (1) total bilirubin (> 33% direct) > 1x ULN to < 3x ULN OR (2) an elevation of AST and/or ALT with normal bilirubin Grade 3 elevation in ALT and/or AST (> 5x ULN)	25% dose reduction. Dose may be re-escalated if liver function tests return to normal and drug-induced hepatotoxicity is excluded.  Hold carfilzomib until resolution to baseline.  Monitor any abnormality weekly. Resume carfilzomib with a 25% dose reduction if drug-induced hepatotoxicity is excluded.
Grade 3 elevation in total bilirubin	Hold carfilzomib until resolution to baseline. Monitor total bilirubin and direct bilirubin weekly.  Upon resolution of total bilirubin to normal, resume carfilzomib dosing with a 25% dose reduction if druginduced hepatotoxicity is excluded.
Drug-induced hepatotoxicity (attributable to carfilzomib)	Discontinue carfilzomib
Thrombotic Microangiopathy (TMA)	If the diagnosis is suspected, hold carfilzomib and manage per standard of care including plasma exchange as clinically appropriate. If TMA is confirmed, permanently discontinue carfilzomib. If the diagnosis is excluded, carfilzomib can be restarted.

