## 10.2 STATISTICAL ANALYSIS OF SECONDARY/EXPLORATORY ENDPOINTS

Secondary endpoints are duration of response and progression free survival (both biochemical progression and progression to overt symptomatic multiple myeloma). Duration of response is defined as time from response to disease progression or death. Progression free survival is defined as time of study entry to progression or death. Duration of response and progression free

*Version Date:* 01/01/2024

survival will be estimated using the Kaplan-Meier and log-rank methods. Secondary endpoints will also include rate and duration of MRD-negative CR and OS.

A number of correlative studies will be performed in order to assess carfilzomib in vitro biological activity and investigate minimal residual disease in SMM. Minimal residual disease will be further explored using multi-parametric flow cytometry, PCR-based techniques, and advanced imaging.

Beginning with Amendment L (version date 05/17/2018), the secondary objectives will also include:

- 1. To estimate the durable MRD (-) CR rate, estimating the fraction of patients who have an MRD (-) CR for 1 year as a minimum. This fraction will be estimated along with a 95% two-sided confidence interval.
- 2. To compare the outcomes among the 18 patients enrolled in 2014 or earlier to the 32 enrolled in 2017 or later because the diagnostic criteria for SMM vs. MM were revised in 2014 after the 18th patient was enrolled. The MRD (-) CR rates will be compared between these two cohorts of patients using a two-tailed Fisher's exact test. All other comparisons of outcomes between the two cohorts will be interpreted as exploratory and will be done using appropriate non-parametric statistical tests without adjustment for multiple comparisons.
- 3. To obtain and report safety data on all enrolled evaluable patients to fully characterize the safety of the regimen in a modestly large number of subjects treated on one protocol.

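### Section 6.1 leaves the recording of symptom-free, untreated laboratory toxicities to investigator discretion, even when they change treatment, and section 10.2 plans no graded laboratory table as a backstop

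*Combined protocol and SAP*

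**What the plan says.** Section 6.1 is restrictive: "An abnormal laboratory value will be recorded in the database as an AE only if the laboratory abnormality is characterized" by an item on the list that follows. Four items are objective:

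- "Results in discontinuation from the study"
- "Is associated with clinical signs or symptoms"
- "Requires treatment or any other therapeutic intervention"
- association with death or another serious event

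The fifth is the investigator's judgement of clinical importance. The last bullet is not a criterion. It asks for the action taken on study drug once a result is already regarded as clinically significant.

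Section 3.3 lets laboratory values alone change treatment. If the Day 1 neutrophil or platelet limits in 3.3.2.2 are missed, "a new cycle of treatment will not be initiated until the toxicity has resolved". For Grade 3 transaminase or bilirubin elevation, the carfilzomib table in 3.3.3 says "Hold carfilzomib until resolution to baseline".

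Toxicity of the combination is a secondary objective (1.1.2). Section 10.2, item 3, sets out to "fully characterize the safety of the regimen". The AE definition in 8.1.1 includes abnormal laboratory findings, and 6.4 adopts CTCAE 4.0 grading.

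**The concern.** The recording rule and the dose-modification rules use different tests. Section 3.3 asks whether a value has crossed a threshold or grade. Section 6.1 asks whether it had clinical consequences, and does not count a change in study drug among them. A laboratory event can therefore be serious enough to interrupt treatment and still meet none of the objective conditions for entry in the AE database.

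At stake is the reported incidence of some of the regimen's expected toxicities. Section 14.2.2 lists neutropenia, anemia and thrombocytopenia among the most common lenalidomide reactions. The trial treats people who do not have symptomatic myeloma, so readers will weigh the toxicity table heavily. If recording depends on judgement, incidence can be too low, and it can vary with who made the judgement. The primary endpoint, MRD-negative CR, is not affected.

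**Working it through.** The plan states no figure on this point, so the check sets each laboratory-driven action in 3.3 against the 6.1 criteria. Assume an event without symptoms, not serious, in a patient who stays on study.

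| Laboratory event | Action under 3.3 | Objective 6.1 criterion met? |
|---|---|---|
| Day 1 ANC below limit, Grade 3, no fever (3.3.2.2, 3.3.5.1) | Cycle not started, or dose modified | None |
| Day 1 platelets below limit (75 x 10^9/L in cycles 1-8, 50 x 10^9/L later), no transfusion | Cycle not started, or dose modified | None |
| Platelets <25 x 10^9/L, no transfusion (3.3.2.3, 3.3.5.2) | Induction: both drugs held, lenalidomide resumed lower. Extended phase: lenalidomide held, resumed lower if drug related | None clearly; prophylactic anticoagulation is also held, which is arguable |
| Grade 3 ALT/AST or bilirubin (3.3.3) | Carfilzomib held; resumed at 25% lower dose if drug-induced hepatotoxicity is excluded | None |
| Renal trigger, such as creatinine at least 2 x baseline, no dialysis (3.3.3) | Carfilzomib withheld; resumed one level lower if attributable | None |
| In-cycle Grade 4 neutropenia, or Grade 3 with fever (3.3.2.3, 3.3.5.2) | Drug held and filgrastim added | Yes, treatment |

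The first five rows reach the AE data only through the judgement criterion, or if a dose hold is read as a therapeutic intervention, which 6.1 does not say.

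Stopping therapy does not close the gap. Toxicity that does not resolve within the allowed time ends protocol therapy (3.6.1), but it is not listed as an off-study reason (3.6.2). The first 6.1 criterion refers to leaving the study.

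No backstop is planned. Section 10.2 describes no tabulation of graded laboratory values apart from recorded AEs, and none was found elsewhere.

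The raw material for one exists. Under 3.3.7.2, routine panels are drawn on five days of cycle 1 and on Day 1 of cycles 2-8, giving 5 + 7 = 12 scheduled draws over 8 cycles. In the extended phases they are drawn every third cycle. Taking the cycles listed for response assessment in 6.3 (9, 12, 15, 18, 21, 24, 27, 30) gives 8 draws over 24 cycles. Weekly counts after a hold and clinically indicated tests (3.3.7.6) add to these.

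**The case against.** The strongest reply is that 6.1 does not exclude these events. An investigator who has stopped a drug because of a laboratory value will usually regard that value as clinically important, and the last bullet of 6.1 expects such results to come with a report of drug action. Section 3.3 supports this: 3.3.3.2 and 3.3.6.2 call the trigger an adverse event and ask the principal investigator to attribute it, and the renal, liver and extended-phase platelet rules also require a causal judgement. Oversight is shared as well. The team meets about weekly to discuss each patient (7.4.1), and sub-investigators may assess events (8.2).

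This stands, and it sets the limit of the point: capture is discretionary and possibly uneven, not barred. A reader might infer that asymptomatic Grade 3-4 cytopenias in general will be absent from the safety report, or that dose reductions will appear with no AE to explain them. The documents support neither. In-cycle Grade 4 and febrile Grade 3 neutropenia meet the treatment criterion through filgrastim, and the judgement criterion can admit the rest.

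The reply does not remove the discretion. No grade or drug action obliges recording, and whether withholding a drug, or pausing prophylactic anticoagulation, counts as an intervention is left open.

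**Conclusion.** The point holds in a limited form. For afebrile Grade 3 neutropenia, untransfused thrombocytopenia, and symptom-free Grade 3 liver or protocol-triggering renal abnormalities, entry in the AE data rests on judgement. Reported incidence can therefore be biased downward. This assumes events without symptoms, treatment or seriousness, and 6.1 read as written.

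The size cannot be derived. The under-count runs from zero, if the judgement criterion is always used, to every such event, if it never is. A reader might take the 20% floor in 14.2.2 for common lenalidomide reactions, compute 0.20 x 50 = 10 patients for each cytopenia, and treat some share as lost. That figure covers reactions of any grade, and the documents give neither the share that would be symptom-free and untreated nor how often judgement would bring them in.

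A reader might also tie the under-count to the favourable risk-benefit statement in 12.4. On the account in 12.3, that statement draws on earlier phase 1 experience with the combination, not on this trial's AE table.

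**What to change.** In section 10.2, item 3, add a table of worst on-treatment CTCAE 4.0 grade per patient for ANC, platelets, hemoglobin, ALT/AST, bilirubin and creatinine. Derive it directly from the laboratory results, separately for induction and the extended phases, and place it beside the investigator-reported AEs for the same patients. Three details matter:

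- Show all grades, because the renal triggers are defined relative to baseline or by clearance, not by grade.
- Show baseline grade, because 2.1.1.5 permits entry with ANC of 0.5 to below 1.0 K/uL at the investigator's discretion.
- Include unscheduled values where held, and state the draw schedule for each phase so that sparser sampling in the extended phases is not read as lower toxicity.

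Adding grade or drug-action triggers to 6.1 would have little effect now. The study calendar notes that all participants had completed maintenance by February 6, 2023; the protocol version is dated 01/01/2024; and general AE recording ends 30 days after the last dose. The derived table is the operative change.

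The cost is one extra table, with no new tests and no change to any dosing rule. It can still miss nadirs between draws, and the reported toxicity rate may be less favourable.

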## 6.1.1 Long-term follow-up data collection

When patients enter the long-term follow-up period, the following data will be collected:

- adverse events related to Carfilzomib
- survival status which will be collected by phone or clinic visit
- additional cancer therapy received

# 6.1.2 Record Keeping

Complete records must be maintained on each patient; these records will consist of the hospital chart as well as any other outside information obtained from outside laboratories, radiology reports, or physician's records. The primary source documentation will include patient eligibility

Version Date: 01/01/2024

data, patient history, flow sheets (including specialty forms for pathology, radiology, or surgery), an off-study summary sheet, and a final assessment by the treating physician.

# 6.1.3 Forwarding of Patient Data from Other Institutions

Either due to extenuating medical circumstances or for convenience, some patients may elect to have certain routine laboratory studies or protein marker analyses performed at an outside institution between scheduled interval visits to the CRC for this protocol. These results will be forwarded to the Myeloma Research Nurse; the data will be entered into the study database and filed in the medical record. Additional blood or tissue samples drawn on patients enrolled in this protocol between scheduled visits may be forwarded and entered into the database as indicated.

